6.7. Access to Investigational Product after the End of the Study

Assuming continuing development of reldesemtiv in ALS, Cytokinetics has put in place an open label extension study for patients who complete dosing through Week 48 in CY 5031. Participation in the open label extension study is at the discretion of the patient and not a condition of participation in CY 5031.

7. TEMPORARY INTERRUPTION OF STUDY DRUG, DISCONTINUATION OF STUDY DRUG, AND PATIENT CONSENT WITHDRAWAL

Unless a safety concern arises, the investigator should make every effort to keep a patient on study drug for as long as possible during the trial. The degree to which a patient withdraws from the trial varies. There are three types of discontinuation: temporary study drug interruption, permanent study drug discontinuation and patient withdrawal of consent.

7.1. Temporary Study Drug Interruption

Initially, any study drug interruption should be considered temporary unless permanent study drug discontinuation is mandated by the protocol.

A temporary study drug interruption:

- Will be implemented when a predefined safety threshold has been met (see [Section 7.3](#) for Renal Function Monitoring).
- May be considered by the investigator in the case of an AE/SAE or for another reason.

If a temporary study drug interruption occurred because a safety threshold was met, blinded treatment may be resumed at a lower dose as outlined in [Section 7.3](#) (Renal Function Monitoring).

If the study drug was temporarily interrupted because of an AE/SAE that was not felt to be related to study drug, the investigator should make the best effort to resume study drug as soon as practically possible, assuming there are no remaining safety concerns.

If dosing is interrupted for more than 7 consecutive days, based upon clinical judgement, the investigator may choose to see the patient in clinic or via telemedicine prior to study drug resumption.

All temporary study drug interruptions (stop and start dates and times and reason for interruption) should be recorded in the CRF and the Medical Monitor should be notified.

7.2. Permanent Discontinuation of Study Drug

There are two types of permanent discontinuation of study drug:

- Temporary study drug interruption that becomes a permanent discontinuation:
 - After a temporary study drug interruption, if a safety concern for the patient has not stabilized or resolved or if the investigator suspects that study drug may be responsible, the investigator may consider the temporary interruption to be a permanent discontinuation. Permanent discontinuation of study drug should be considered as a last resort.
 - The investigator should make best efforts to contact the Medical Monitor before considering any temporary interruption as a permanent discontinuation.
- Permanent study drug discontinuation that is not preceded by a temporary study drug interruption

- The investigator should make best efforts to contact the Medical Monitor before considering any permanent study drug discontinuation.

In all cases, patients should be encouraged to discuss stopping study drug with the investigator or the investigator's designee. See [Section 6.6](#) regarding potential dose reduction of study drug. Best efforts should be made to address the patient's questions, adjust concomitant medical therapies if needed and arrange follow-up safety assessments. All patients should undergo an early discontinuation visit as soon as possible following their last dose taken, unless discontinuation is due to death, withdrawal of consent, or the patient has been lost to follow-up. Refer to [Section 7.2.1](#) for management of patients that permanently discontinue study drug.

Any permanent discontinuation of study drug should be recorded in the CRF including the reason for permanent discontinuation, if a patient is willing to provide it. If the patient is unwilling to provide the reason, that too should be documented.

Reasons for permanent study drug discontinuation may include any of the following:

- Patient request
- Adverse event
- Pregnancy
- Criteria for possible renal toxicity are met ([Section 7.3](#))
- Criteria for possible hepatotoxicity are met ([Section 7.4](#))
- The investigator judges that continued administration of study drug would be detrimental to the patient's safety or well-being
- Protocol violation
- Lost to follow-up
- Any breaking of the study blind requested by the investigator
- Death
- The Sponsor requests that the patient permanently discontinue study drug

7.2.1. Management of Patients after Permanent Discontinuation of Study Drug

If study drug is permanently discontinued, the patient should be encouraged to remain in the trial to continue to obtain outcome measures and safety data.

There are several options for a patient after permanently discontinuing study drug:

- Patient agrees to continue to return to clinic for all remaining in-clinic study visits and agrees to all planned remote visits.
- Patient only agrees to complete the early discontinuation (ED) visit as soon as possible after the decision is made, the follow-up visit 4 weeks after the last dose taken, and additional follow-up visits dependent upon lab results; it is preferred these are done in clinic but can be done remotely if that is not feasible.

- Patient only agrees to complete the ED visit; it is preferred this is done in clinic but can be done remotely if that is not feasible.
- Patient only agrees to remote visits to obtain patient study data. Patients should be strongly encouraged to come into the clinic for Week 24.
- Patient agrees to a mix of remote and in-clinic visits to obtain study data. Patients should be strongly encouraged to come into the clinic for Week 24.
- Patient only agrees to allowing contact for determination of vital status at Week 24 and Week 48
- Patient withdraws consent (see [Section 7.6](#)) and does not agree to any further study procedures or visits.

Assessments obtained at the early discontinuation and subsequent follow-up visit are listed in the Schedule of Activities. Details of the assessments to be performed at the additional visits following drug discontinuation, should the patient agree to be followed via either in-clinic or remote visits, can be found in the Study Manual.

Patients that have not withdrawn consent and have difficulty returning for all remaining study visits can be contacted by phone or video call to obtain patient study data.

7.3. Renal Function Monitoring and Study Drug Management

Study drug will be held if:

- $eGFR_{Cr}$ and $eGFR_{CysC} < 30.0$ ml/min/1.73m² or
- urine protein creatinine ratio (UPCR) is ≥ 3 mg protein/mg creatinine (or ≥ 339 mg protein/mmol creatinine)

Study drug may be restarted at half the dose, or 1 tablet twice a day (150 mg bid for those assigned to reldesemtiv) when:

- $eGFR_{Cr}$ and $eGFR_{CysC}$ is > 40.0 ml/min/1.73m² and
- UPCR is ≤ 1.5 mg protein/mg creatinine (or ≥ 170 mg protein/mmol creatinine)

Serum cystatin C, $eGFR_{CysC}$, serum creatinine, $eGFR_{Cr}$ and urine protein/creatinine ratio in a spot urine will be obtained and a microscopic urinalysis will be performed to look for cells and casts in accordance with the schedule of events; the medical monitors will be blinded to the UPCR (and the associated urinary creatinine and urinary protein), creatinine, serum cystatin C, $eGFR_{CysC}$, and $eGFR_{Cr}$ results. These renal related laboratory results will be reviewed by an unblinded physician who is not serving as the medical monitor for the trial. The unblinded physician will be unmasked to the renal lab results but will remain blinded to treatment assignments. The unblinded physician will contact the clinical trial investigator and medical monitors if laboratory results meet the criteria as described above that necessitate a study drug interruption. The Sponsor, all personnel charged with conduct of the trial outside of monitoring these laboratory data, and study sites will be blinded to the UPCR (and the associated urinary creatinine and urinary protein), creatinine, serum cystatin C, $eGFR_{CysC}$, $eGFR_{Cr}$ results.

Abnormal renal function tests meeting the above criteria will be repeated as directed by the unblinded physician, who will monitor repeat testing. The site investigator and medical monitors should discuss and agree that study drug can be resumed or alternatively permanently discontinued. Agreement by the patient, site investigator, and medical monitor must occur to determine that:

1. The study drug may be re-initiated at the lower dose of 150 mg bid (or placebo), or
2. The study drug should be permanently discontinued

To accomplish this, the unblinded physician may direct the laboratory assessments (serum cystatin C, eGFR_{CysC}, serum creatinine eGFR_{Cr}, UPCR) to be repeated as often as 2-3 times weekly until a final disposition is reached (ie, re-initiation of study drug or placebo at 150 mg bid or permanent discontinuation) is reached.

Manifestations of renal toxicity, including clinically significant decreases in eGFR_{CysC} and eGFR_{Cr}, as well as increases of UPCR, as noted above, are considered adverse events of special interest and should be recorded on the appropriate CRF and reported to Cytokinetics Drug Safety within 24 hours of awareness.

Criteria for permanent discontinuation of study drug due to potential renal toxicity

Study drug **must** be discontinued permanently if the patient requires hemodialysis.

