Patients must interrupt study drug for certain specified laboratory abnormalities. Hepatic related interruptions are permanent discontinuations. For renal related laboratory abnormalities, the interruption continues until the laboratory value in question has returned to the threshold specified in the protocol for re-initiation of treatment. Patients may then resume dosing at 1 table twice a day thereafter (150 mg twice daily). Patients also may be down-titrated to 1 tablet twice a day by the Investigator in the case of adverse events felt to be related to study drug. Once patients have been down-titrated to one tablet twice daily for any reason, their dose may not be returned to two tablets twice daily.

Data Monitoring Committee:

An independent Data Monitoring Committee (DMC) will periodically assess patient safety in an unblinded manner during the course of the trial.

Interim Analyses:

Twelve (12) weeks after approximately one-third or more of the planned sample size is randomized, the first interim analysis may be triggered. Its purpose is to determine if there is a lack of effect of reldesemtiv on the ALSFRS-R in CY 5031, a finding that would be inconsistent with the prior observed effect on the change from baseline at 12 weeks in ALSFRS-R total score in the Phase 2 trial, CY 5022. At this interim analysis, the DMC will receive unblinded efficacy data from the independent, third-party biostatistical group supporting them and assess the effect of reldesemtiv on the change from baseline to Week 12 in the ALSFRS-R total score. At this interim assessment, if the treatment difference for change from baseline to Week 12 in ALSFRS-R total score has a one-sided p-value larger than or equal to 0.5 (ie, the estimated treatment difference of the change from baseline at Week 12 in ALSFRS-R total score is favoring placebo), the DMC may recommend stopping the trial due to futility. This futility analysis based on the data of change from baseline to Week 12 in ALSFRS-R will not have any alpha spending in the final analysis of the trial. The Sponsor will monitor the blinded aggregate standard deviation of the change from baseline to Week 12 in ALSFRS-R total score periodically and possibly adjust the specified p-value before this interim analysis is conducted.

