5.2. Exclusion Criteria

Patients will be excluded from the trial if any of the following criteria apply:

201. Other medically significant neurological conditions that could interfere with the assessment of ALS symptoms, signs or progression.
202. Presence at screening of any medically significant cardiac, pulmonary, gastrointestinal, musculoskeletal, or psychiatric illness that might interfere with the patient's ability to comply with study procedures or that might confound the interpretation of clinical safety or efficacy data, including, but not limited to:
 - a. Poorly controlled systemic hypertension
 - b. Clinically significant electrocardiogram (ECG) abnormalities that require medical attention (ie, persistent atrioventricular conduction block $>$ first degree, or acute myocardial ischemic changes)
 - c. New York Heart Association Class II or greater congestive heart failure
 - d. Chronic obstructive pulmonary disease
 - e. Gastrointestinal disorder that is likely to impair absorption of study drug from the gastrointestinal tract
 - f. $eGFR_{Cr}$ and $eGFR_{CysC} < 45.0$ mL/min/1.73 m² at screening
 - g. ALT or AST $\geq 3 \times$ ULN at screening
 - h. Urine protein creatinine ratio > 1 mg/mg (113 mg/mmol) at screening
 - i. Total bilirubin (TBL), direct or indirect bilirubin above the ULN.
 - j. History of Gilbert's Disease, Dubin-Johnson syndrome, or Rotor syndrome
 - k. Poorly controlled or brittle diabetes mellitus
 - l. Amputation of a limb
 - m. Cognitive impairment, related to ALS or otherwise that impairs the patient's ability to understand and/or comply with study procedures and provide informed consent
 - n. Cancer currently being treated (other than basal cell carcinoma, carcinoma in situ of the cervix, or squamous cell carcinoma of the skin excised with clean margins) or a history of cancer with an expected survival of less than 5 years. Breast cancer survivors with an expected survival of ≥ 5 years who are on long-term endocrine therapy are eligible.
 - o. Any other condition, impairment or social circumstance that, in the opinion of the Investigator, would render the patient not suitable to participate in the trial
 - p. Patient judged to be actively suicidal or a suicide risk by the Investigator
203. Known to have received reldesemtiv or tirasemtiv in any previous clinical trial

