6.3. Measures to Minimize Bias: Randomization and Blinding

All patients will be centrally assigned to randomized study drug using an Interactive Web Response System (IWRS). Before the trial is initiated, the log in information & directions for the IWRS will be provided to each site.

Study drug will be dispensed at the study visits summarized in the SoA ([Section 1.3](#)). Returned study drug should not be re-dispensed to the patients.

The IWRS will be programmed with blind-breaking instructions and the unblinding procedure is documented in the IWRS User Manual. In case of an emergency, the investigator has the sole responsibility for determining if unblinding of a patient's treatment assignment is warranted. Patient safety must always be the first consideration in making such a determination. If the investigator decides that unblinding is warranted, the investigator should make every effort to contact Cytokinetics prior to unblinding a patient's treatment assignment unless this could delay emergency treatment of the patient. If a patient's treatment assignment is unblinded, Cytokinetics must be notified within 24 hours after breaking the blind. The date and reason that the blind was broken must be recorded in the source documentation and CRF, as applicable.

An unblinded physician (unmasked to renal labs but blinded to treatment assignments) who is not on the study team may direct a study drug interruption and a down-titration of patients based upon review of unmasked renal function laboratory values that meet the prespecified criteria ([Section 6.6](#) and [Section 7.3](#)). In order to preserve blinding of site staff and the study operation team, a small number of placebo patients will be selected for dummy down-titration during the study by the unblinded Clinical Research Organization (CRO) physician and will undergo repeat laboratory testing similar to what could be directed for patients receiving active treatment with laboratory abnormalities. The blinded down-titration selection criteria and records will be documented by the unblinded physician and the unblinded statistician separately. In order to maintain the blind, placebo patients who had a dummy down-titration during the double-blind dosing period will take 150 mg bid of reldesemtiv during the active drug period.

The randomization treatment assignments for individual patients will remain blinded to site staff and patients until the entire study is completed and the database is locked.

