**Test product, dose and mode of administration:**

Reldesemtiv will be administered as 150 mg tablets, at a dose of 300 mg twice a day for a 600 mg TDD. Reldesemtiv tablets will be taken orally.

Patients must interrupt study drug for certain specified laboratory abnormalities. Hepatic related interruptions are permanent discontinuations. For renal related laboratory abnormalities, the interruption continues until the laboratory value in question has returned to the threshold specified in the protocol for re-initiation of treatment. Patients may then resume dosing at 1 tablet twice a day thereafter (150 mg twice daily). Patients also may be down-titrated to 1 tablet twice a day by the Investigator in the case of adverse events felt to be related to study drug. Once patients have been down-titrated to one tablet twice daily for any reason, their dose may not be returned to two tablets twice daily. A physician unblinded to renal laboratory results directs drug interruptions due to renal lab findings.

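### Protocol 7.3: the UPCR restart limit after a renal hold has its inequality reversed in the mg/mmol form (≥ 170 printed where ≤ 170 is meant)

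*Protocol*

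**What the plan says.** Section 7.3 of the protocol has a hold rule and a restart rule for renal laboratory values.

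- **Hold:** both eGFRs below 30.0, or "urine protein creatinine ratio (UPCR) is ≥ 3 mg protein/mg creatinine (or ≥ 339 mg protein/mmol creatinine").
- **Restart at one tablet twice daily:** both eGFRs above 40.0 and "UPCR is ≤ 1.5 mg protein/mg creatinine (or ≥ 170 mg protein/mmol creatinine").

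Exclusion criterion 202h in Section 5.2 supplies the unit conversion: "Urine protein creatinine ratio > 1 mg/mg (113 mg/mmol) at screening".

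The Synopsis states the purpose of the restart rule: "the interruption continues until the laboratory value in question has returned to the threshold specified in the protocol for re-initiation of treatment". The SAP's Technical Summary Report repeats this but gives no figure, so Section 7.3 is the only place in either document where the UPCR restart limit is stated.

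On who applies the limit, Section 7.3 says "the medical monitors will be blinded to the UPCR (and the associated urinary creatinine and urinary protein") and extends the blind to the sponsor and sites. The results go to a physician outside the study team who sees renal values but not treatment. Section 6.3 has that physician act on "review of unmasked renal function laboratory values that meet the prespecified criteria", and the SAP says "A physician unblinded to renal laboratory results directs drug interruptions due to renal lab findings". The decision to resume or stop for good is shared: "Agreement by the patient, site investigator, and medical monitor must occur to determine that" one or the other applies.

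**The concern.** The two halves of the UPCR restart limit are offered as equivalents but point in opposite directions. One asks that proteinuria has fallen to the limit, the other that it is at or above it. Both units are printed as valid, and the protocol does not say which governs or which the laboratory reports.

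Two kinds of patient are affected if the mg/mmol form is followed:

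- **Held for proteinuria alone, both eGFRs above 40.0.** UPCR is then the only laboratory value in the restart rule that stands between the patient and renewed dosing, and the printed mg/mmol form is met by values that have not recovered.
- **Held for eGFR alone, now recovered above 40.0, UPCR below 170.** The two parts of the rule are joined by 'and', so the literal mg/mmol form refuses restart to a patient who should qualify.

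The blinding makes this harder to catch. The investigator and medical monitor must agree to a restart but cannot compare the UPCR with the limit; only the physician who sees the renal results can. Section 2.3.1.1 relies on Section 7.3 as part of the renal risk mitigation, so its limits need to be unambiguous.

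**Working it through.** **Inputs**

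- Conversion: 1 mg/mg = 113 mg/mmol (Protocol 5.2, criterion 202h).
- Hold limit: ≥ 3 mg/mg, printed equivalent ≥ 339 mg/mmol (Protocol 7.3).
- Restart limit: ≤ 1.5 mg/mg, printed equivalent ≥ 170 mg/mmol (Protocol 7.3).

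**Step 1: reproduce the printed figures** (mg/mmol = mg/mg × 113)

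- Hold: 3 × 113 = 339. This matches, and the sign is the same in both units.
- Restart: 1.5 × 113 = 169.5, which rounds to the printed 170. The number matches; the sign does not.

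**Step 2: can any value meet both printed restart forms?**

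The printed mg/mmol form needs at least 170/113 = 1.504 mg/mg. The mg/mg form allows at most 1.5. The two sets do not overlap.

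**Step 3: apply each form to specific values**

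| UPCR, mg/mg | UPCR, mg/mmol | Hold rule met | Restart, ≤ 1.5 mg/mg | Restart as printed, ≥ 170 mg/mmol | Restart corrected, ≤ 170 mg/mmol |
|---|---|---|---|---|---|
| 0.2 | 22.6 | no | yes | no | yes |
| 1.0 (highest allowed at entry) | 113 | no | yes | no | yes |
| 1.5 | 169.5 | no | yes | no | yes |
| 1.51 | 170.6 | no | no | yes | no |
| 2.0 | 226 | no | no | yes | no |
| 3.0 | 339 | yes | no | yes | no |
| 3.54 | 400 | yes | no | yes | no |
| 4.0 | 452 | yes | no | yes | no |

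The printed mg/mmol column is the opposite of the mg/mg column in every row. The corrected column agrees with it in every row. Between 169.5 and 170 mg/mmol a rounding gap of 0.004 mg/mg remains, which has no practical meaning.

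**Step 4: which direction is intended?**

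- The hold bullet uses one direction for both units, so the restart bullet is the odd one out.
- The paired eGFR limits require recovery: hold below 30.0, restart above 40.0.
- The Synopsis and SAP say the interruption lasts until the value is back at the threshold.
- Section 7.3 counts rises in UPCR as renal toxicity.

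All four point to ≤.

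**Step 5: the range left exposed**

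At 339 mg/mmol and above, the correctly printed hold rule still applies. The values that the printed mg/mmol form wrongly admits, and that the hold rule does not block, run from 170 to below 339 mg/mmol (1.504 to below 3 mg/mg). The 226 mg/mmol row is an example.

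**The case against.** The strongest reply is that this is a slip with obvious intent and several safeguards around it.

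- **The correct limit is printed first.** To go wrong, the reviewing physician would have to follow the parenthesis, ignore the mg/mg figure beside it, and accept that more proteinuria qualifies for restart. That is unlikely in a one-off reading. It is less unlikely if an alert or instruction sheet was copied from the mg/mmol form.
- **The hold rule is mandatory and restart is only permitted.** This stands: values of 339 and above remain blocked, and the exposure is confined to the range in step 5. It does nothing for recovered patients who would be refused.
- **There is other oversight.** The DMC includes a nephrologist and has patient-level data (Section 10.1.5), renal tests may be repeated two to three times a week, and renal toxicity must be reported within 24 hours. These limit the consequence, but none is described as a check on an individual patient before restart.
- **The text was read from a PDF by a program, and the point rests on one character.** A misread cannot be fully excluded. The neighbouring signs in the same bullets read sensibly, and a look at the source page settles it.
- **Whether the error reached practice is unknown.** It depends on instructions and alerts that are not part of these documents.

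These points limit how serious the error is. None makes the printed limit correct.

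**Conclusion.** The concern holds: the mg/mmol form of the UPCR restart limit is wrong as written. This is an operative dosing threshold in a safety rule, stated only once, so it should be fixed, although the intended meaning is clear.

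The conclusion rests on the protocol's own conversion factor and on the sign having been read correctly from the PDF. It concerns only the UPCR part of the restart rule; the eGFR condition and the three-party agreement still apply. The documents do not say how often UPCR triggers a hold, and none is assumed. No effect on sample size, alpha, power or the primary analysis is claimed.

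**What to change.** In the restart rule of Protocol Section 7.3, replace ≥ 170 with ≤ 170 mg protein/mmol creatinine. Then confirm that the written instructions of the physician who reviews the renal results, and any laboratory alerts, apply the limit in that direction.

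The cost is a one-character protocol correction and that check. Design, sample size and analysis are unchanged, and the SAP needs no edit because it only refers to the protocol's threshold.
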